covered in this IND application. That IRB trial would allow up to five years follow up on subjects and would only allow investigators to observe how the subject is doing long term, whichever treatment options the subject pursues in consultation with their regular doctor in that time. That planned follow up protocol will allow Stanford to contact the subjects several times a year in order obtain information about any therapy they may elect to follow, including sildenafil if their regular doctor prescribes it, and their response to any therapy.

Multi-Center:

Yes

Number of Centers:

Up to 4

Blinding:

|                |     |
|----------------|-----|
| Observer-Blind | Yes |
| Subject-Blind  | Yes |
| Double-Blind   | Yes |

Randomization:

Group Assignment Ratio: 2:1 randomization of two subjects who receive sildenafil to one subject who receives placebo.

Concurrent Control:

No other treatments for lymphatic malformation will be allowed except antibiotics and/or surgical drainage if the lesions become infected. Treatment for recurrent infections in the lymphatic malformation will be allowed and documented during the trial. Concurrent medications will be documented. Subjects who require sclerosing agents or excisional surgery of their lymphatic malformation will be withdrawn from the trial.

Variable(s): PRIMARY: Change in lesion volume over twenty weeks of the test medication as evaluated by MRI examination. Comparison of placebo to sildenafil treated subjects.

SECONDARY: Change in lesion volume estimated using a soft tape measure to measure the length, width, and hemispheric measurement of each of the lymphatic malformations. (Berk, Berk et al. 2011) Completion of the form *Lymphatic Malformation Measurements*.

Subject's evaluation of the change in lesion clinical characteristics from baseline to 20 weeks by examining decreased discomfort, texture or thickness, distortion of normal anatomy or overall change obtained in the subject's

completion of *Subject's Assessment of Lymphatic Malformation Change* form.

Physician's evaluation of the lesion clinical characteristics on the day of the visit. This includes color, tenseness and texture, superficial component, deep component, and distortion of anatomical landmarks. This requires completion of the *Lymphatic Malformation Assessment* form for each LM site.

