#### **7.1.6. Week 20 [ ± 21 days before or after scheduled visit] at Stanford**

End of Treatment for subjects treated with sildenafil. Possible commencement of treatment for those subjects on placebo.

1. Query subject and/or caregiver regarding any changes in general health and the use of concomitant medications. Obtain demographic information and review interim medical history, including information on all medications currently being taken. Review previous concomitant medications and current concomitant medications. Instruct the subject and/or caregiver of the excluded medications and give them a list if they do not have their list with them.
2. If any adverse events are observed or reported, they must be recorded as instructed in Section 13, Adverse Events.
3. Ophthalmology evaluation, hearing exam, and blood draw performed. Subjects from cooperating research study sites will have the option to do these tests at their local site or at Stanford.
4. Perform a physical examination including heart and pulmonary auscultation, liver and spleen palpation, abdominal auscultation and palpation, and documentation of

peripheral pulses. Examine and describe the characteristics of their lymphatic malformation.

5. Obtain Vital Signs including height, weight, temperature, heart rate, blood pressure, respiratory rate, oxygen saturation.
6. Clinical assessment of each lymphatic malformation including measuring the hemicircumference of the lesion by using a soft measuring tape placed on the skin over the area of the widest diameter of the lesion. The length, and width, will then be calculated as describe in Figure 2 of Berk et al (2011). In order to document the site of the measurements a diagram will be drawn by hand or photographs will be taken of the methods. Each clinic visit will try to duplicate the measurements methods used in the initial visit.
7. Photographs of the Lymphatic malformation will be taken using standardized procedures described in Baseline Visit.
8. Completion of subject's evaluation of the change in lesion clinical characteristics from baseline, such as decreased discomfort, texture or thickness, distortion of normal anatomy or overall change obtained in the subject's completion of *Subject's Assessment of Lymphatic Malformation Change* form.

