9. Completion of the physician's evaluation of the lesion clinical characteristics on the day of the visit. This includes color, tenseness and texture, superficial component, deep component, and distortion of anatomical landmarks. This requires completion of the *Lymphatic Malformation Assessment* form for each LM site.
10. Physician's evaluation of the change in lesion clinical characteristics from baseline, such as change in texture or thickness, change in distortion of normal anatomy, and over change in lesions. This requires completion of the *Lymphatic Malformation Assessment of Change* form for each LM site.
11. Collect study drug and perform compliance assessment; medication journal reviewed.
12. Obtain a pregnancy test if the subject is has achieved menarche.
13. The participant or parent/guardian and the investigator will complete the qualitative assessment of efficacy. The subject's evaluation of the response to the treatment will be reviewed. The results report of the MRI done at the twenty week visit will be shared with the subject and compared with the initial MRI reported results. After that discussion the subject will be told if they were on sildenafil or placebo. Subjects who received placebo will be given the option to start the sildenafil. Subjects who received active medication will be requested to stop the sildenafil for the next twelve weeks and follow up at the 32 week visit to examine the response of the lesion off of the sildenafil.

14. If subject received placebo and decides to receive sildenafil at this time, the study medication dose will be calculated and obtained from the pharmacy for adequate study medication to last until the next visit in 4 weeks. The 2 hour monitoring will be completed after the first dose as described in Baseline visit. For more detail, see Section 7.1.7. If the subject was on placebo and elects not to start sildenafil they will not need to return for the 32 week evaluation.
15. If the subject received placebo and decides to not receive sildenafil they will end the study at this time and complete additional information needed for the End of study 32 week visit described in 7.1.7. below.
16. If a subject approves, we will send a copy of the dictated record for the study visit to their local primary care doctor and /or pediatric dermatologist so that the physicians in their home community are aware of the study and the subject's participation in the study.

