**7.1.9. Weeks 2 Active, 8 Active, and 16 Active [ ± 1 day]**

These phone calls will follow the same procedures described in Section 7.1.4.

**7.1.10. Weeks 4 Active and 12 Active [ ± 14 days before or after scheduled visit] at subject's cooperating research site for subjects who are on placebo for the initial twenty weeks of the trial**

These visits will follow the same procedures described in Section 7.1.5.

**7.1.11. Week 20 Active [End of Treatment, ± 21 days before or after scheduled visit] at Stanford for subjects who are on placebo for the initial twenty weeks of the trial**  
This visit will follow the same procedures described in Section 7.1.6, except that there is no unblinding and no option to start a treatment period of active sildenafil.

**7.1.12. Week 32 Active [ End of Study, ± 2 Weeks] at subject's cooperating research site for subjects who are on placebo for the initial twenty weeks of the trial**  
This visit will follow the same procedures described in Section 7.1.7.

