**7.1.13. Early Exit at subject's cooperating research site or at Stanford**

In addition to the procedures required at the EOT visit:

1. The subject will be exited from the study.
2. Study medication will be collected. The subject may elect to not return to Stanford or the cooperating research site for this visit. In this case, we will have them mail the unused medication back to Stanford. We will give them pre-addressed shipping forms. If the subject does not return for this visit, we may also arrange to get the pregnancy test at a local hospital or local office.

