**7.2. DISCONTINUED SUBJECTS**

Discontinued subjects are those who voluntarily discontinue participation, who are withdrawn for safety reasons or use of prohibited concomitant treatments, or who have missed a sufficient number of study visits, procedures or test medication doses as to be ineligible for further participation.

All subjects who discontinue the study prior to completing the regularly scheduled visits must complete the EOT and Exit Visit procedures described in Section 7.1.11. Any changes in medical health and/or the use of concomitant treatments must be captured. If any adverse events were observed since the previous visit, they must be recorded

(refer to Section 13, Adverse Events). Finally, if appropriate, the Investigator also should advise the subject's parent or legally authorized representative of subsequent therapy and/or procedures necessary for their medical condition.

In the case of subjects who persistently fail to return for scheduled visits, three attempts must be made to contact the subject's parent or legally authorized representative for the purpose of scheduling an Exit/EOS Visit. The third attempt should be via registered mail, return receipt requested.

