## **10. STATISTICAL DESIGN**

### **10.1. EVALUABILITY**

All subjects who receive study medication will be evaluable for the safety analysis. All subjects who receive study medication will be evaluable for the intent-to-treat analysis.

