| Hearing exam                                  | x             |  |   |  |   |  |   | x                                       |   |
| Administer and dispense study medication      |                             | x  |   | x  |   | x  |   |   |   |
| Monitor vital signs every 30 mins for 2 hours |                             | x  |   |  |   |  |   |   |   |
| Collect unused study medication               |                             |  |   | x  |   | x  |   | x   |   |
| Dispense or review medication diary           |                             | x  |   | x  |   | x  |   | x   | x   |
| End of treatment                              |                             |  |   |  |   |  |   | x   |   |
| MRI   | x                           |  |   |  |   |  |   | x   |   |
| Review adverse events                         |                             | x  | x   | x  | x   | x  | x   | x   | x   |
| Unblind treatment                             |                             |  |   |  |   |  |   | x                                       |   |
| End of study/ Exit form                       |                             |  |   |  |   |  |   |   | x   |

 The "-A" suffix at end of Visit name indicates visits that are for the crossover Active Treatment Period, an option offered to any subject who received placebo during the Original Treatment Period.

 At Week 20, treatment will be unblinded and if subject received placebo then they have the option to enter the Active Treatment Period. Unblinding is performed only at the Week 20 Visit of the Original Treatment Period.

 If subject is female who has reached menarche.

 If hearing exam is not successful at screening, it will be repeated at subsequent visits until a satisfactory hearing test result is obtained.

 Subjects who exit early will not have a final MRI but we will attempt to obtain a Urine Pregnancy Test.

 Subjects local to a cooperating research site will attend Week 4, Week 12, and Week 32 visits at their cooperating site.

 Subjects local to a cooperating research site will be offered the option to have this procedure at their cooperating site or at Stanford.

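### Table 16-1 footnote 5 gives early exits no final MRI while Sections 7.1.13 and 7.2 require the end-of-treatment procedures, so the primary outcome may go unmeasured in subjects the plan counts as evaluable

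*Combined protocol and SAP*

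**What the plan says.** The primary variable is change in MRI lesion volume over 20 weeks, sildenafil against placebo (Synopsis; Section 10.2.1). Section 10.1 defines the analysis set: "All subjects who receive study medication will be evaluable for the intent-to-treat analysis". Section 10.2 says the same for efficacy.

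On subjects who leave early, the plan speaks in three places:

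- Table 16-1, footnote 5: "Subjects who exit early will not have a final MRI but we will attempt to obtain a Urine Pregnancy Test".
- Section 7.1.13 introduces the exit steps with "In addition to the procedures required at the EOT visit".
- Section 7.2 says that subjects who discontinue "must complete the EOT and Exit Visit procedures described in Section 7.1.11".

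Section 7.1.11 refers onward: "This visit will follow the same procedures described in Section 7.1.6". Its only exceptions are unblinding and the option to start active drug. Section 7.1.6 item 13 takes the MRI as part of that visit: "The results report of the MRI done at the twenty week visit will be shared with the subject". Item 3 adds the safety tests: "Ophthalmology evaluation, hearing exam, and blood draw performed".

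The Synopsis names one reason for leaving that is tied to the lesion itself: "Subjects who require sclerosing agents or excisional surgery of their lymphatic malformation will be withdrawn from the trial".

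**The concern.** The footnote and the body text point in different directions on whether the primary outcome is collected after early withdrawal. A site following the footnote would not scan. A site following Sections 7.1.13 and 7.2 would have reason to.

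If the footnote governs, the stated intent-to-treat comparison becomes in practice a comparison of those who reached the Week-20 MRI. Sections 10 and 11 give no rule for a missing MRI. The linear mixed model in Section 7.4.3 does not fill the gap even if applied to MRI volume: the double-blind period has two MRI time points, so an early exit contributes a baseline and nothing after it.

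The loss need not be random. A placebo child whose lesion grows and who goes to excision would leave the comparison, which makes the remaining placebo group look better. Loss of sildenafil non-responders would make sildenafil look better. If loss is equal in both arms and unrelated to lesion change, only precision suffers. The same outcome would presumably inform the efficacy and futility looks after 15, 30 and 45 subjects in Section 11, so the study's exploratory label does not make the point idle.

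**Working it through.** **No plan figure to reproduce.** Section 11 has no power calculation, and the documents state no dropout rate, SD or effect size. The check is a comparison of texts, followed by illustrative ranges.

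**1. Does the MRI belong to the end-of-treatment visit?** It is not a numbered step of Section 7.1.6. Three places nevertheless put it there: Section 6.1 repeats the MRI at the 20-week visit, item 13 of 7.1.6 refers to the scan done at that visit, and Table 16-1 marks both MRI and end of treatment in the Week-20 column. An instruction to complete the end-of-treatment procedures therefore reasonably includes it.

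**2. Do Sections 7.1.13 and 7.2 depend on a doubtful cross-reference?** The pointer from 7.2 to 7.1.11 may be stale numbering, since 7.1.5 item 4 sends Early Exit to 7.1.12 although it now stands at 7.1.13. The result does not change, because 7.1.13 itself asks for the end-of-treatment procedures.

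**3. Who is affected?** Only subjects who leave the double-blind period before the Week-20 MRI. A subject who leaves later already has that scan.

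**4. Room for loss.** The goal of 40 completers with an MRI and the enrolment of up to 60 come from Section 5.1. The 55 starting medication comes from the Synopsis.

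- 60 − 40 = 20; 20/60 = 33%.
- 55 − 40 = 15; 15/55 = 27%.

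These are ceilings implied by the targets, and they mix uncertain recruitment with dropout. I therefore assume 5 to 20 lost of 60.

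**5. Precision**, assuming loss keeps the 2:1 ratio. Ratio of standard errors = √(planned / measured).

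- 55 of 60 measured: √(60/55) = 1.04, up 4%.
- 40 of 60 measured: √(60/40) = 1.22, up 22%.

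**6. Bias**, assuming the same leaver-to-completer gap in both arms. The full mean in an arm is the completers' mean plus share lost × gap, so

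shift = (share lost on placebo − share lost on sildenafil) × gap.

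- Low assumption: 0.10 × 0.5 SD = 0.05 SD.
- High assumption: 0.30 × 1.0 SD = 0.30 SD.
- Standard error with all 60 measured (40 v 20): √(1/40 + 1/20) = 0.27 SD.

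**7. One example.** Lost: 5 of 20 placebo and 4 of 40 sildenafil, gap 1 SD.

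- Shift: (0.25 − 0.10) × 1 = 0.15 SD.
- Standard error for the remaining 36 v 15: √(1/36 + 1/15) = 0.307 SD.
- Shift in standard errors: 0.15/0.307 = 0.49.

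**The case against.** The strongest reply is that footnote 5 is a deliberate exception. It is the only text that addresses the MRI in early exits, and a specific note can override a general cross-reference. Section 7.1.13 allows exit at a cooperating site or no return at all, and the only test it arranges for non-returners is the pregnancy test, which matches the footnote. For families at other sites both MRIs are at Stanford (Section 6.1). Section 7.1.5 item 15 has the scan arranged from an earlier visit.

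Much of this stands: no MRI may well be the intent. But the footnote drops the scan for every early exit, including those who attend, while 7.1.13 limits its fallback to those who do not return. If the exception is intended, 7.1.13 and 7.2 should say so, and the primary outcome is then missing by rule with no method for handling it.

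A reader might also infer from the blank Early Exit cells that laboratory, eye and hearing tests are not wanted. The table does not support that. Early Exit shares the Week-32 column, and the pregnancy test and collection of unused medication are blank there too, although footnote 5 and 7.1.13 call for them. The case for those tests rests on 7.1.6 item 3, not on the blanks.

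Finally, an exit scan at an early week is not a 20-week change, so pooling it without comment would be open to dispute. That limits what an exit scan recovers and is reflected in the fix.

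**Conclusion.** The texts disagree, and the footnote is the reading that does harm: followed as written, it leaves every subject who exits before the Week-20 MRI without the primary outcome, while Sections 10.1 and 10.2 keep that subject in the analysis set. This should be settled.

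Three stronger readings go beyond the documents:

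- That 15 to 20 subjects will be lost. Those are ceilings from enrolment targets; no dropout rate is given, and accrual may stop at an interim look.
- That the result will be biased in a known direction. Loss could favour either arm or neither.
- That footnote 5 is plainly an error. It may be intended.

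The 4% to 22% loss of precision and the 0.05 to 0.30 SD shift rest on assumed numbers lost, an assumed difference in loss between arms and an assumed leaver-to-completer gap. They show only that the effect could range from negligible to about one full-data standard error (0.30 against 0.27 SD).

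**What to change.** Replace footnote 5: a subject who leaves the double-blind period early and is willing to return is asked to have the final MRI, at the Week-20 time if feasible and otherwise at exit, and before any sclerotherapy or excision. Mark the MRI and the end-of-treatment laboratory, eye and hearing tests for Early Exit in Table 16-1, keeping the local-site option for those three tests.

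Add to Section 10.2.1:

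- the exit MRI is used in the intent-to-treat comparison, with its study day recorded;
- subjects with no final MRI are listed by arm and reason;
- a sensitivity analysis varies their assumed change, reported beside a completers-only analysis.

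If the sponsor prefers to keep the exception, Sections 7.1.13 and 7.2 should state it, and the last two items are still needed.

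Cost: one footnote, four table marks and a paragraph. The scans, 5 to 20 at most under the assumption above, replace Week-20 scans already planned for the same subjects. Some families would have to travel to Stanford, some scans will still be missing because a family may decline to return, and exit scans will cover less than 20 weeks.

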## 17. APPENDICES

### 17.1. LABORATORY TESTS

Laboratory tests will be obtained upon entry (baseline) and end of treatment into the clinical trial. The exams will include:

- Complete Blood Count:  
Hematocrit  
Hemoglobin  
White Blood Cell Count (WBC)  
WBC differential  
Red Blood Cell Count (RBC)  
MCV (Mean Corpuscular Volume)  
MCH (Mean Corpuscular Hgb)  
MCHC (Mean Corpuscular Hgb Concentration)  
RDW (RBC distribution width)  
Stained Red Cell examination (Peripheral Smear)  
Platelet Count
- Complete Metabolic Panel:  
Albumin  
Alkaline Phosphatase Total  
ALT  
AST  
Urea Nitrogen  
Calcium  
Chloride  
CO2 Content  
Creatinine  
Glucose  
Globulin  
Potassium  
Sodium  
Total Bilirubin  
Total Protein  
Anion Gap
- Urine Pregnancy if required (See Schedule of Events)

### 17.2 INSTRUCTIONS OF ORAL SUSPENSION FOR PHARMACIST

### 17.2.1 Instructions for Pharmacist (2 pages)

page 1:

|   |
|---|
| 
INSTRUCTIONS FOR PHARMACIST FOR
COMPOUNDING REVATIO® 20MG TABLETS
 
Compounding of an extemporaneously prepared oral suspension from <del>Revatio®</del> 20 mg film-coated tablets (final concentration 10 mg/ml). Compounding of an oral suspension, by a pharmacist, following this procedure, will provide one patient with enough medicinal product for a: 28-day course of treatment (1 ml dosing volume, 10 mg dose) or a 14-day course of treatment (2 ml dosing volume, 20 mg dose).
 
Ingredients:
 
The compounding of the <del>Revatio®</del> oral suspension from <del>Revatio®</del> 20 mg tablets uses <del>Ora-Sweet</del> and <del>Ora-Plus</del> diluents.
 
Compounding instructions for a pharmacist:
 

1. Ensure <del>Ora-Sweet</del> and <del>Ora-Plus</del> have been equilibrated to room temperature.

2. Count 62 (sixty two) x 20 mg <del>Revatio</del> tablets.

3. Using a mortar and pestle, crush these 62 tablets, 2-10 tablets at a time, into a fine powder.

4. Measure out 30 ml <del>Ora-Plus</del> (cloudy white liquid), allowing time for any air bubbles to dissipate.

5. Add a portion (15-20 ml typical) of <del>Ora-Plus</del> from step 4 to the mortar and mix into a thick homogeneous paste. More <del>Ora-Plus</del> from step 4 may be added if necessary.

6. Transfer the paste to an amber glass or <del>high density</del> polyethylene (HDPE) bottle (<math>\geq</math> 150 ml volume)

7. Rinse the mortar and pestle with the remaining <del>Ora-Plus</del> from step 4 and transfer <del>rinses</del> to the bottle to ensure complete transfer of the paste.

8. Measure 90 ml <del>Ora-Sweet</del> (clear pink liquid) allowing time for any air bubbles to dissipate.

9. Transfer approximately half of the volume of the <del>Ora-Sweet</del> from step 8 to the bottle containing the formulation prepared above.

10. Cap bottle and shake vigorously for a minimum of 30 seconds.

11. Transfer the remaining <del>Ora-Sweet</del> from step 8 to the bottle and shake vigorously

 |
|---|

page 2:

INSTRUCTIONS FOR PHARMACIST FOR

COMPOUNDING REVATIO® 20MG TABLETS

again for a minimum of 30 seconds to achieve a homogenous oral suspension.

12. Put an ancillary label on the bottle warning "Patients with rare hereditary problems of fructose intolerance, glucose-galactose malabsorption or sucrase-isomaltase insufficiency, should not take this medicinal product". The ancillary label should also indicate "Shake well for a minimum of 10 seconds before each dosing". Include the patient's name, dosing instructions, expiry date, and medicinal product name.

13. Instruct the person who is to administer the compounded product that any remaining material following completion of therapy must be discarded by either affixing an ancillary label to the bottle or adding a statement to the pharmacy label instructions.

14. Place an appropriate expiration date label according to storage condition.

Consider dispensing the oral suspension with an appropriate graduated oral dosing syringe for measuring the required volumes of oral suspension.

If possible, mark or highlight the graduation corresponding to the appropriate dose (1 ml or 2 ml) on the oral dosing syringe for each patient.

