## 2. SYNOPSIS

Study Phase: 2

Financial Disclosure Information for U.S. FDA Submission to be Obtained? Yes

Test Medication: Sildenafil 20 mg tablets, 2.5mg/ml suspension (Revatio®)  
Control Medication: Placebo tablets or suspension resembling Revatio®

Study Dosage / Usage: Oral dosage of sildenafil. For pediatric patients 8 kg to 20 kg the suspension/tablets dose will be 10 mg/4ml three times a day (30 mg per day) and for patients > 20 kg the dose is 20 mg/8ml three times a day (60 mg a day). Subjects less than 8 kg will not be enrolled in the trial.

Route of Administration: The medication will be given orally. The subjects who will receive the 10 mg dose will be given an oral suspension (using dose calculation by the study pharmacist) or half a tablet. Subjects will have the option of taking tablets or receiving an oral suspension of the medication in 2.5mg per mL.

Objective(s): The objectives of this study are to assess the safety and effectiveness of sildenafil taken orally to improve or resolve lymphatic malformations.

Study Population: Sixty Subjects (60)

Subjects will be between the ages of 6 months to 10 years of age inclusive with lymphatic malformations (LM) that have a **minimum diameter of 3 centimeters** based upon MRI evaluation. Based on the patient numbers in pediatric dermatology clinics over the country, we expect that we will be able to screen 60 patients who will meet the inclusion criteria, and 55 patients will be enrolled in the study and begin medication. After 15 subjects are completed, an interim analysis will be performed to project effect size and estimate the total number of subjects required for the study. If after analysis of 15, 30 or 45 subjects we find that we are in the range of futility or efficacy, then we will notify the FDA as well as the DSMB, and begin to end the study by adding no additional subjects.

Structure: Double-blind trial of placebo compared to sildenafil with an open label extension for subjects who received placebo. Two to one ratio of two sildenafil treated subjects who

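### Appendix 17.2 holds two sets of pharmacist compounding instructions that differ fourfold in concentration and dosing volume, and nothing states which applies

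*Combined protocol and SAP*

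**What the plan says.** **Section 17.2.1** describes a suspension compounded from "film-coated tablets (final concentration 10 mg/ml"). It says that one batch covers a "28-day course of treatment (1 ml dosing volume, 10 mg dose) or a 14-day course of treatment (2 ml dosing volume, 20 mg dose"). The recipe is "Count 62 (sixty two) x 20 mg" tablets, then "Measure out 30 ml" of Ora-Plus, then 90 ml of Ora-Sweet. It suggests a syringe mark: "If possible, mark or highlight the graduation corresponding to the appropriate dose (1 ml or 2 ml) on the oral dosing syringe". Its label step asks for the patient's name, "dosing instructions, expiry date, and medicinal product name". It names only the active tablet.

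**The Synopsis** says that for children of 8 to 20 kg "the suspension/tablets dose will be 10 mg/4ml three times a day (30 mg per day"), with 20 mg in 8 ml three times a day above 20 kg. It offers the option of "receiving an oral suspension of the medication in 2.5mg per mL".

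**Section 4.2** directs the study pharmacist to formulate at 2.5 mg per ml. For 8 to 20 kg it specifies a 480 ml batch divided into four 120 ml bottles as a 4-week supply. Above 20 kg it also calls for a 4-week supply. It keeps the subject and research physician blinded until the Week 20 visit.

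**Section 17.2.2** has two sheets under the study title, both at 2.5 mg/ml and both covering sildenafil or placebo: 105 tablets to 840 ml (20 mg in 8 ml) and 60 tablets to 480 ml (10 mg in 4 ml). The vehicle is equal parts of the two diluents.

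**Cross-references.** Section 4.3 sends the reader to 17.1 for compounding, which is the laboratory test list. Section 7.1.3 (step 10) points to Section 18.2, but Section 18 is the Declaration of Helsinki statement and has no subsections.

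**The concern.** A pharmacist who opens Appendix 17.2 finds two preparations with different strengths, volumes and vehicles, and no statement of precedence. The stated dose is reached only if concentration and volume come from the same place.

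There is a plausible route to mixing them. The 17.2.2 sheets end with shaking the bottle and contain no step for a patient label or a syringe. The only syringe instruction in the document is in 17.2.1, at 1 or 2 ml. Someone who compounds by 17.2.2 and turns to 17.2.1 for the syringe would mark a quarter of the volume that goes with that bottle. In the other direction, fill volume would not give the error away: a 17.2.1 batch is about 120 ml, the same as each of the four bottles in Section 4.2.

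An error one way is a safety matter in small children. The other way it is lost exposure in the active arm, which would bias the MRI volume comparison towards no effect.

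Blinding is a secondary point. If 17.2.1 were used for active drug while placebo followed 17.2.2, volume and vehicle would differ by arm. A product name on the bottle, as 17.2.1 asks, is not in the label list of Section 4.2 and sits badly with the blinding described there.

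**Working it through.** **1. Stated concentrations, reproduced** (tablets × 20 mg ÷ volume)

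- 17.2.1: 62 × 20 = 1,240 mg. Vehicle is 30 + 90 = 120 ml. 1,240 ÷ 120 = 10.3 mg/ml, against a stated 10. It is exactly 10 at a final volume of 124 ml, so the stated figure is reasonable.
- 17.2.2, 20 mg sheet: 105 × 20 ÷ 840 = 2.5 mg/ml, as stated.
- 17.2.2, 10 mg sheet: 60 × 20 ÷ 480 = 2.5 mg/ml, as stated.
- Ratio of stated concentrations: 10 ÷ 2.5 = 4.

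**2. Dose delivered** (concentration × dosing volume)

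| Bottle made by | Volume taken from | Dose in mg | Against stated 10 / 20 mg |
|---|---|---|---|
| 17.2.1 | 17.2.1 (1 / 2 ml) | 10 × 1 = 10; 10 × 2 = 20 | same |
| 17.2.2 | 17.2.2, Synopsis, 4.2 (4 / 8 ml) | 2.5 × 4 = 10; 2.5 × 8 = 20 | same |
| 17.2.1 | 17.2.2, Synopsis, 4.2 (4 / 8 ml) | 10 × 4 = 40; 10 × 8 = 80 | 4 times |
| 17.2.2 | 17.2.1 (1 / 2 ml) | 2.5 × 1 = 2.5; 2.5 × 2 = 5 | one quarter |

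Each source is self-consistent. Only the last two rows go wrong.

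**3. Would supply reveal a mix-up?** (three doses a day)

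- Fourfold case, one 17.2.1 batch of about 120 ml: 120 ÷ (4 × 3) = 10 days, or 120 ÷ (8 × 3) = 5 days. The bottle runs out early.
- Fourfold case, four such batches made to fill the four bottles: 4 × 120 = 480 ml, and 480 ÷ 12 = 40 days at 4 ml. There is no early run-out.
- Quarter case, whole 17.2.2 batch dispensed (assumption), remainder at day 28: 480 − 28 × 3 × 1 = 396 ml, or 840 − 28 × 3 × 2 = 672 ml. Under the stated volumes it would be 480 − 28 × 3 × 4 = 144 ml, or 840 − 28 × 3 × 8 = 168 ml. The Week 4 drug count could show that surplus, but that visit has a window of ± 14 days.

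**4. Other differences**

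- Ora-Plus to Ora-Sweet: 30:90 = 1:3 in 17.2.1; 420:420 and 240:240 = 1:1 in 17.2.2.
- Supply at the 20 mg dose: 17.2.1 states 14 days per batch, and 120 ÷ (2 × 3) = 20 days at most. Section 4.2 calls for 4 weeks.

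**5. Does the text settle precedence?** No passage withdraws 17.2.1 or ranks the two. The machine-read text shows strike-through on isolated words in 17.2.1 (product and diluent names and a few others), but not on the concentration, tablet count, volumes or steps. This looks like an extraction artefact, and the source PDF can confirm it.

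**The case against.** The strongest reply is that 17.2.1 is evidently a generic product sheet left in the appendix, and that the operative text points one way:

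- Section 4.2 directs 2.5 mg per ml, and its 480 ml batch matches the 60-tablet sheet.
- Only 17.2.2 carries the study title, calls for the study tablets and covers placebo. As written, 17.2.1 cannot supply a blinded placebo arm.
- Every source gives the same 10 mg or 20 mg, so the fourfold figures come from no single instruction.
- Safeguards exist: one central pharmacy, a checker column in 17.2.2, a first dose taken in clinic with vital signs every 30 minutes for 2 hours, a Week 2 call (the Synopsis says the calls ask about medication taken), and drug counts at Weeks 4 and 12. If only one 17.2.1 batch were dispensed, a fourfold error would empty the bottle by day 5 or 10, before the Week 2 call.
- The wrong cross-references fit a general numbering drift. Adverse events are cited as Section 13 but are in Section 12, and the procedures table is cited as 17-1 but is 16-1.

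Much of this stands. The text is not neutral, harm needs cross-use, and a prolonged error is unlikely. The label and vehicle points are minor: Section 4.2 does not say that its label list is exhaustive, and the documents give no consequence for the vehicle ratio.

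It does not remove the conflict. A checker facing two unranked instructions has no single standard to check against. Section 4.3, the section that refers the pharmacist onward, speaks of film-coated tablets, a term found in 17.2.1 and not in 17.2.2, although 4.3 also mentions placebo. Even if the 18.2 pointer is read as 17.2, it lands on the heading that contains both sets. Early run-out would not reveal the quarter-dose case, nor a fourfold case in which several batches were made.

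**Conclusion.** The concern holds, and the passages must be reconciled. Two current compounding instructions differ by a factor of 4 in concentration and in dosing volume. The size of the possible error is 40 or 80 mg per dose in one direction and 2.5 or 5 mg in the other, against the stated 10 or 20 mg. These figures are conditional on a bottle made by one instruction being dosed by the volume of the other, and they use the stated concentrations (10 and 2.5 mg/ml). No probability of such a mix-up can be derived from the documents. The finding rests on the milligram doses being as stated throughout and on 17.2.1 being in force, which its place in the contents and the lack of any withdrawal support. It ranks as a required correction because this is an operative preparation instruction for children from 8 kg, not background text.

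**What to change.** - Reconcile 17.2.1 with the Synopsis, Section 4.2 and Section 17.2.2, so that one concentration, one set of dosing volumes and syringe marks, and one vehicle apply to active and placebo alike.
- Remove any sheet that does not apply, or mark it clearly as not in use.
- Put the label and syringe steps on the sheet that governs, with label text compatible with the blinding in Section 4.2.
- Correct the cross-references in Sections 4.3 and 7.1.3 so that both lead to that sheet.

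The sponsor and study pharmacy must settle which strength and volume apply; this review takes no position. The cost is protocol and appendix wording only, with no effect on design, sample size or analysis.
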